#### 8.4.6. Pregnancy

Female participants who become pregnant after administration of the study intervention may continue the study at the discretion of the investigator.

- Details of all pregnancies in female participants will be collected after the start of study intervention and until the last visit (Day 183).
- If a pregnancy is reported, the investigator will record pregnancy information on the appropriate form and submit it to the sponsor within 24 hours of learning of the female participant pregnancy.
- Any pregnancy complication or elective termination of a pregnancy for medical reasons will be reported as an AE or SAE.

- Abnormal pregnancy outcomes (e.g., spontaneous abortion, fetal death, stillbirth, congenital anomalies, ectopic pregnancy) are considered SAEs and will be reported as such.
- The participant will be followed to determine the outcome of the pregnancy. The investigator will collect follow up information on the participant and the neonate and the information will be forwarded to the sponsor. See [Table 17](#) for reporting timeframes.
- Any post-study pregnancy-related SAE considered reasonably related to the study intervention by the investigator will be reported to the sponsor as described in Section [8.4.4](#). While the investigator is not obligated to actively seek this information in former study participants, he or she may learn of an SAE through spontaneous reporting.
- Any female participant who becomes pregnant post-dosing while participating in the study will be allowed to continue the study until the end unless she withdraws consent or the investigator decides that it is in the participant's best interest to be discontinued from the study.

#### **8.4.8. Participant card**

The investigator (or designee) must provide the participant with a “participant card” containing information about the clinical study. The participant must be instructed to always keep the participant card in their possession for the duration of the study. In an emergency, this card serves to inform the responsible attending physician/caregiver/family member that the participant is in a clinical study and that relevant information may be obtained by contacting the investigator(s) or their back up.

## **8.4.9. Medical device deficiencies**

Medical devices are being provided for use in this study as part of the study intervention. To fulfill regulatory reporting obligations worldwide, the investigator is responsible for the detection and documentation of events meeting the definitions of device deficiency that occur during the study with such devices.

The definition of a medical device deficiency can be found in Section [10.5](#).

NOTE: Deficiencies fulfilling the definition of an AE/SAE will follow the processes outlined in Section [10.5](#) of the protocol.

### **8.4.9.1. Time period for detecting medical device deficiencies**

- Medical device deficiencies that result in an incident will be detected, documented, and reported during all periods of the study in which the medical device is used.
- If the investigator learns of any device deficiency at any time after a participant has been discharged from the study, and such a deficiency is considered reasonably related to a medical device provided for the study, the investigator will promptly notify the sponsor.

The method of documenting medical device deficiencies is provided in Section [10.5](#).

### **8.4.9.2. Follow up of medical device deficiencies**

- Follow up applies to all participants, including those who discontinue study intervention.
- The investigator is responsible for ensuring that follow up includes any supplemental investigations as indicated to elucidate the nature and/or causality of the deficiency.
- New or updated information will be recorded on the originally completed form with all changes signed and dated by the investigator.

### **8.4.9.3. Prompt reporting of device deficiencies to the sponsor**

- Device deficiencies will be reported to the sponsor within 24 hours after the investigator determines that the event meets the protocol definition of a medical device deficiency.
- The medical device deficiency report form will be sent to the sponsor by email. If email is unavailable, then fax should be utilized.
- The sponsor will be the contact for the receipt of device deficiency reports.

**8.4.9.4. Regulatory reporting requirements for device deficiencies**

- The investigator will promptly report all device deficiencies occurring with any medical device provided for use in the study in order for the sponsor to fulfill the legal responsibility to notify appropriate regulatory authorities and other entities about certain safety information relating to medical devices being used in clinical studies.
- The investigator, or responsible person according to local requirements (e.g., the head of the medical institution), will comply with the applicable local regulatory requirements relating to the reporting of device deficiencies to the IRB/IEC.

**8.5. Pharmacokinetics**

PK is not evaluated in this study.

**8.6. Pharmacodynamics**

Pharmacodynamics is not evaluated in this study.

**8.7. Genetics**

Genetics are not evaluated in this study.

**8.8. Biomarkers**

Section is not applicable.

**8.9. Immunogenicity assessments**

Immunogenicity is described in Section [8.2](#)

**8.10. Health economics**

CCI

CCI

## 9. STATISTICAL CONSIDERATIONS

The statistical analysis plan will be finalized prior to the first subject first visit and it will include a more technical and detailed description of the statistical analyses including demography, tertiary endpoint analyses and supporting analyses, if applicable. This Section is a summary of the planned statistical analyses of the most important endpoints, i.e., the primary endpoints.

### 9.1. Statistical hypotheses

There is no formal hypothesis testing in this study; where statistical methods are applied, the emphasis will be on estimation with 95% CIs.

### 9.2. Analysis sets

Analysis set	Description
Screened	All participants who were screened for eligibility
Enrolled	All participants who entered the study (who were randomized or received study intervention or underwent a post-screening study procedure). Note: screening failures (who never passed screening, even if rescreened) and participants screened but never enrolled into the study (met eligibility but not needed) are excluded from the Enrolled analysis set as they did not enter the study
Exposed Set (ES)	All participants who received a study intervention. Analysis per group is based on the study intervention administered
Per Protocol Set (PPS)	All eligible participants who received the dose of study intervention as per protocol, had immunogenicity results pre- and Day 29 post-dosing, without intercurrent conditions (influenza disease) that may interfere with immunogenicity and without prohibited concomitant medication/vaccination before Day 29. The analysis will be done according to the study intervention that participants received. Results from blood sample deviating from the dosing/blood draw intervals (refer to Table 3 and Table 4 ) as well as results obtained after intercurrent conditions (influenza disease, new malignancy and immunocompromised condition ) that may interfere with immunogenicity or after prohibited concomitant medication/vaccination during this period will be excluded from the PPS.

### 9.3. Statistical analyses

The co-primary and secondary endpoints are described in Section 3. The primary analyses of immunogenicity endpoints will be based on the PPS. The analysis of reactogenicity and safety endpoints will be based on the ES. All analyses will be done separately for OAs and YAs according to study phase, unless specified otherwise.

### 9.3.1. Co-primary reactogenicity and safety endpoints

The percentage of participants reporting each individual solicited administration site event (any grade, Grade 2 or 3, Grade 3 and medically attended events) and solicited systemic event (any grade, Grade  $\geq 2$ , Grade  $\geq 3$  and medically attended events) within the 7-day follow up period (i.e., Day 1-Day 7 post-dosing) will be tabulated for each group.

The verbatim reports of unsolicited AEs will be reviewed by a qualified person and the signs and symptoms will be coded according to the Medical Dictionary for Regulatory Activities (MedDRA) Dictionary for Adverse Reaction Terminology. Every verbatim term will be matched with the appropriate PT. The percentage of participants with any unsolicited AEs within the 28-day follow up period (i.e., Day 1-Day 28 post-dosing) with its exact 95% confidence interval (CI) will be tabulated by group and by MedDRA PT and System Organ Class (SOC). Similar tabulation will be done for Grade 3 unsolicited AEs, for any causally related unsolicited AEs, for Grade 3 causally related unsolicited AEs and for unsolicited AEs resulting in a medically attended visit.

The percentage of participants with at least 1 report of SAE, with at least 1 report of MAE and with at least 1 report of AESI, respectively, classified by the MedDRA SOC and PT and reported from Dose 1 up to study end will be tabulated with exact 95% CI.

The percentage of participants using concomitant medication (any medication, any antipyretic and any antipyretic taken prophylactically, respectively) during the 28-day follow up period (i.e., Day 1 - Day 28 post-dosing) will be summarized by group.

#### 9.3.1.1. Analysis of reactogenicity: Bayesian Logistic Regression Model (BLRM)

An adaptive BLM will be used to inform on the posterior probability of the true Grade 3 solicited event rate for all dose levels used in Phase 1 study groups. The use of Bayesian response adaptive models for Phase 1 studies has been advocated by the European Medicines Agency (EMA) adopted guideline on small populations [EMA, 2006] and by Rogatko et al. [Rogatko, 2007] and is one of the key elements of the FDA's Critical Path Initiative.

The 2-parameter BLM described by Neuenschwander et al., 2008 [Neuenschwander, 2008] will be used to assess reactogenicity and recommend the mRNA doses to proceed to Phase 2 of the study.

Standardized dose level will be used such that one of the doses ( $d^*$ ) equals 1, e.g., doses are rescaled as  $d/d^*$ . Consequently,  $\alpha$  is equal to the odds of the probability of intolerance at  $d^*$ . This model was shown to be fit for purpose in the context of Phase 1 mRNA vaccine dose range [Walsh, 2020; Kremsner, 2021]. The prior distribution will be updated after each group of participants with all the data available in the Safety Set from the current study. Once updated, the distribution summarizes the posterior probability that the true Grade 3 solicited event rate for each dose level lies in the following categories:

- 0% to <18%: targeted tolerance; and

- $\geq 18\%$  to 100%: intolerance.

The principle of the BLRM mandates that any dose of the study vaccine candidates that has more than a 50% chance of being in the intolerance category is not considered for the next dose administrations [Neuenschwander, 2008; Babb, 1998].

Section 10.7 provides additional details on the model and data scenarios.

A clinical synthesis of the available safety and reactogenicity information (including symptoms that are not Grade 3), and, if available, laboratory values as well as the recommendations from the Bayesian model and the *SRT/iSRC* or iDRC (Refer to Section 10.1.6 for the *SRT*, *iSRC* and iDRC roles) will be used to select the investigational study intervention for Phase 2. The frequency of each safety event associated to holding rules (see Table 13) will be tabulated by study group (i.e., by dose level and formulation). Individual data will also be available.

### 9.3.2. Co-primary and secondary immunogenicity endpoints

At each phase, the group difference between the investigational study intervention formulation, and dose level and the control group will be assessed separately as follows for CCI [REDACTED]:

- At each post-dosing timepoint separately, the 2-sided CI for group GMT ratio between investigational study intervention dose and (over) the control group will be derived from an ANCOVA model on  $\log_{10}$  transformed concentration. The ANCOVA model will include group (i.e., each of the investigational study intervention and the control group), actual age of participants, country, flu vaccination history and  $\log_{10}$ -transformed concentration at pre-dosing as fixed effects. The adjusted GMT and GMI in each group will be obtained from the same model with 95% CI. Missing data will not be replaced. Concentrations below the assay lower level of quantification (LLOQ) will be replaced by half the assay LLOQ.
- For a given age group, the 2-sided 95% CI on group difference in SCR between an investigational study intervention and (minus) the control group will be computed at Day 29 based on the method of Miettinen and Nurminen [Miettinen, 1985].
- For CCI [REDACTED] only: the percentage of participants achieving seroprotection, defined as having post-dosing CCI [REDACTED] will be summarized by age group with associated exact 95% CI.

All analyses will be performed separately for each age group, where applicable.

Abbreviation/term	Definition
GMI	The geometric mean of the ratios of the post-dosing titer over the Day 1 titer.
CCI	The percentage of dosed participants who have either a pre-dose CCI [REDACTED] and a post-dosing CCI [REDACTED] or a pre-dose CCI [REDACTED] and at least a 4-fold increase in post-dosing CCI [REDACTED].
	The percentage of dosed participants who have either a pre-dose CCI [REDACTED] and a post-dosing CCI [REDACTED] or a pre-dose CCI [REDACTED] and at least a 4-fold increase in post-dosing NI titer.
SPR (seroprotection rate)*	The percentage of dosed participants with a CCI [REDACTED].
S+ (seropositive)	Titer $\geq$ LLOQ

CCI [REDACTED]

## 9.4. Interim analyses

### 9.4.1. Sequence of interim and other planned analyses

In addition to the analyses detailed below, additional analyses e.g., safety analyses, may be conducted to support the *SRT*, iSRC and iDRC decisions, as described in Section 8.3.7.1. Refer to Section 10.1.6 for the *SRT*, iSRC and iDRC roles.

Two interim analyses are foreseen and will be conducted upon availability of all primary endpoints up to Day 29 for participants in Phase 1 and Phase 2, respectively. CCI [REDACTED].

*For the observer-blinded Phase 2 interim analyses, a restricted study team will be unblinded to individual participant data and all efforts will be made to ensure the participants, investigators and monitoring staff blinding is maintained up to study end. The rest of the study team will have access to group data but will remain blinded to individual participant data and treatment assignment until the end of the study. It is possible, however, due to the limited sample size, that unblinding occurs for a few participants having a specific AE or SAE (e.g., an AE/SAE occurring only in a single participant). Therefore, anyone having access to the results could become unblinded regarding those few specific cases.*

An analysis with all primary and secondary endpoints obtained until the last visit (Day 183) will be performed and made available to the investigators and submitted to regulatory authorities, as appropriate. This may be performed separately for each phase.

Analysis of tertiary endpoints may be performed at a later stage. Tertiary analyses deemed futile due to the other study results will not be analyzed nor reported.

### 9.4.2. Statistical considerations associated with the interim analyses

As this study is descriptive and each analysis will be completed on expected final immunogenicity data, there will be no type I error adjustment for the different analyses. All interim analyses will be based on the ES.

## 9.5. Sample size determination

Enrolled participants who withdraw from the study will not be replaced.

### 9.5.1. Sample size determination for Phase 1

The study is designed to provide a reasonable precision for the rate of Grade 3 solicited events and to describe the safety profile of an mRNA-based vaccine.

For each investigational study intervention group, it is expected that 24 participants will be enrolled. Assuming a maximum acceptable rate of Grade 3 solicited events of 18%, it is possible to calculate the probability of a lower true Grade 3 solicited event rate given a different number of participants with Grade 3 solicited event(s). [Table 19](#) provides the estimate and 95% credibility interval for a given observed number of participants for a sample size of 24 participants per study group (assuming a Beta [0.5,0.5] prior distribution). For example, if 4 participants report Grade 3 solicited event(s) among 24 exposed participants, the posterior probability that the true Grade 3 solicited event rate is <18% is 54.5%.

**Table 19 Posterior probability estimates of Grade 3 solicited event rate <18% for different observed numbers of participants with Grade 3 solicited event(s) and 95% credibility interval for the rate**

Number of participants with Grade 3 solicited event(s)	Estimate (95% credibility interval) in %	Probability Grade 3 solicited event rate <18%
0	2 (0 - 9.8)	99.8
1	6 (0.5 - 17.9)	97.6
2	10 (1.8 - 24.1)	89.9
3	14 (3.6 - 29.7)	74.8
4	18 (5.9 - 34.9)	54.5

A further description of the BLRM, including prior, hypothetical data scenarios of number of Grade 3 solicited events that could occur in the actual study, and the decision guides are presented in Section [10.7](#).

### 9.5.2. Sample size determination for Phase 2

The primary objective is to explore how the different formulation(s) or dose level(s) of mRNA-based vaccine compare to licensed control group(s).

The sample size of **108** evaluable participants in each dose level cohort and age group, is expected to provide a 95% CI for group difference in SCR with a *lower* half-width below 12% for difference in seroconversion rates for the different strains ([Table 20](#)) and a 95% CI with an expected half-width of **1.36** fold for the group geometric mean concentration ratio considering a population standard deviation of **0.5** in  $\log_{10}$  transformation concentration post-dosing and 5% of unevaluable participants per group.

**Table 20 Half-width of 95% CI for the group difference in seroconversion rates by to control and strain (Evaluable N per group = 108)**

Control	Strain	Proportion (%) *	95% CI of Proportion (%)	Lower Half-width of 95 CI (%)
CCI				

\*Obtained from meta-analysis of historical data from CCI

CCI  
[REDACTED].

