4.8. Changes to Protocol Defined Analyses

The BLRM described on Section 4.2.1.5 has been modified to include 2 slope parameters accounting separately for the total amounts of CCI [REDACTED] in each formulation which deviates from that specified in the protocol amendment 1 (Dated: 07 April 2023) where only one slope accounting for the sum of total amounts of both CCI [REDACTED] in each formulation was planned. To focus the laboratory testing, only participants exposed to mRNA vaccines with CCI [REDACTED] in the formulation and control group will be included in the subset for CCI [REDACTED] testing. In CCI [REDACTED]

Section 5.2 is updated to reflect the actual unevaluable rate and lower half-width used for Phase 2 sample size estimation.

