5. SAMPLE SIZE DETERMINATION

5.1. Sample Size Determination for Phase 1

The study is designed to provide a reasonable precision for the rate of Grade 3 solicited events and to describe the safety profile of an mRNA-based vaccine. For each investigational study intervention group, it is expected that 24 participants will be enrolled. Assuming a maximum acceptable rate of Grade 3 solicited events of 18%, it is

possible to calculate the probability of a lower true Grade 3 solicited event rate given a different number of participants with Grade 3 solicited event(s). [Table 7](#) provides the estimate and 95% credibility interval for a given observed number of participants for a sample size of 24 participants per study group (assuming a Beta [0.5,0.5] prior distribution). For example, if 4 participants report Grade 3 solicited event(s) among 24 exposed participants, the posterior probability that the true Grade 3 solicited event rate is <18% is 54.5%.

Table 7 Posterior probability estimates of Grade 3 solicited event rate <18%

Number of participants with Grade 3 solicited event(s)	Estimate (95% credibility interval) in %	Probability Grade 3 solicited event rate <18%
0	2 (0 - 9.8)	99.8
1	6 (0.5 - 17.9)	97.6
2	10 (1.8 - 24.1)	89.9
3	14 (3.6 - 29.7)	74.8
4	18 (5.9 - 34.9)	54.5

A further description of the BLRM, including prior, hypothetical data scenarios of number of Grade 3 solicited events that could occur in the actual study, and the decision guides are presented in Section 10.7 of the protocol.

5.2. Sample size determination for Phase 2

The primary objective is to explore how the different formulation(s) or dose level(s) of mRNA-based vaccine compare to licensed control group(s).

The sample size of 108 evaluable participants in each dose level cohort and age group, is expected to provide a 95% CI for group difference in SCR with a lower half-width below 13.3% for difference in seroconversion rates for the different strains ([Table 8](#)) and a 95% CI with an expected half-width of 1.36-fold for the group geometric mean concentration ratio considering a population standard deviation of 0.5 in log10 transformation concentration post-dosing and 10% of unevaluable participants per group.

Table 8 Half-width of 95% CI for the group difference in seroconversion

Control	Strain	Proportion (%)	95% CI of Proportion (%)*	Lower half-width of 95% CI (%)
CCI				

*Obtained from meta-analysis of historical data CCI

CCI

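### Protocol 9.5.2 gives a 5% unevaluable rate that its own 120 and 108 contradict, and a seroconversion half-width below 12% that SAP 5.2 replaces with 13.3%

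*Protocol*

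**What the plan says.** Protocol section 4.1 plans about 960 participants in eight Phase 2 groups, 120 per group. Section 9.5.2 and the title of Table 20 use 108 evaluable per group. For that number, section 9.5.2 gives:

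- a lower "half-width below 12% for difference in seroconversion rates for the different strains";
- a 1.36-fold half-width for the geometric mean concentration (GMC) ratio, with a log10 standard deviation of 0.5;
- "5% of unevaluable participants per group".

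SAP section 5.2 (SAP Amendment 4, based on Protocol Amendment 2) keeps 108 evaluable, a standard deviation of 0.5 and 1.36-fold. It differs on the other two values, giving a "lower half-width below 13.3% for difference in seroconversion rates" and "10% of unevaluable participants per group". SAP section 4.8, which lists changes to protocol-defined analyses, states: "Section 5.2 is updated to reflect the actual unevaluable rate and lower half-width used for Phase 2 sample size estimation".

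Protocol section 9.3.2 plans "the 2-sided 95% CI on group difference in SCR", "based on the method of Miettinen and Nurminen". Section 9.1 states: "There is no formal hypothesis testing in this study". The strain-specific rates in protocol Table 20 and SAP Table 8 are redacted.

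**The concern.** Two current documents give different loss rates and different SCR precision for the same number of evaluable participants. The protocol's loss rate also fails against the protocol's own group sizes.

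Phase 2 has no hypothesis test, so expected interval width is the stated justification for its immunogenicity sample size. The protocol and its amendments go to ethics committees and, where required, to health authorities (protocol section 10.1.1). Someone who reads only the protocol sees a narrower SCR interval and half the planned loss that the SAP says was used. The author of the study report would find two figures for one design.

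**Working it through.** **Inputs.** From the protocol: 120 enrolled per group (4.1); 108 evaluable, SD 0.5 on the log10 scale, 1.36-fold, 5%, below 12% (9.5.2); two-sided 95% Miettinen-Nurminen interval (9.3.2). From the SAP: 10% and below 13.3% (5.2). Assumption: because the strain rates are redacted, the SCR is taken as equal in the mRNA and control groups and varied from 20% to 80%.

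**1. The figure that reproduces: GMC ratio.** The half-width is 10^(1.96 × SD × √(2/n)).

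- n = 108: 1.96 × 0.5 × √(2/108) = 0.1334, and 10^0.1334 = 1.359, which rounds to the stated 1.36.
- n = 114: 10^0.1298 = 1.348, which rounds to 1.35.

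So 108 is the number on which the protocol's precision was computed.

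**2. Unevaluable rate.**

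- 120 × 0.95 = 114, not 108.
- 108 / 0.95 = 113.7, so 114 would need to be enrolled, not 120.
- 1 − 108/120 = 0.10, and 108 / 0.90 = 120.

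The 10% in the SAP connects 120 and 108; the 5% in the protocol does not. This step uses no redacted value.

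**3. SCR half-width.** The lower limit is the value d below the observed difference that solves (p1 − p2 − d) / √V(d) = 1.96. Here V(d) is the variance under the constrained maximum-likelihood rates at difference d, multiplied by N/(N − 1) with N = 2n. The lower half-width is (p1 − p2) minus that limit. With p1 = p2:

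| Common SCR | n = 108 | n = 114 | n = 120 |
|---|---|---|---|
| 20% or 80% | 10.80% | 10.51% | 10.23% |
| 25% or 75% | 11.60% | 11.29% | 11.00% |
| 28% or 72% | 11.99% | 11.67% | 11.38% |
| 30% or 70% | 12.22% | 11.90% | 11.59% |
| 40% or 60% | 13.00% | 12.66% | 12.34% |
| 50% | 13.25% | 12.90% | 12.58% |

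At n = 108 the 12% line is crossed at rates of 28.05% and 71.95%. A half-width below 12% therefore requires every strain to lie at or beyond about 28% or 72%. The equal-rate maximum of 13.25% fits the SAP's bound of 13.3%. A true 5% loss (n = 114) would still give 12.90% at 50%. Keeping the half-width below 12% at every common rate would take about 132 evaluable per group.

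**4. Sensitivity to equal rates.** At n = 108, 60% against 50% gives 13.29%, 60/108 against 48/108 gives 13.36%, and 90% against 50% gives 11.38%. So 13.25% is the maximum for equal rates, not an absolute one.

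**The case against.** The strongest reply is that the sponsor has already found this. SAP 5.2 carries both revised values, SAP 4.8 and the SAP version history declare the change, and protocol section 9 describes itself as a summary with detail left to the SAP. That stands, and it reduces the point to a protocol sentence that was not brought into line.

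A second reply is that 108 per group does not by itself refute a half-width below 12%, because the bound refers to strain rates that cannot be seen. That also stands: with every strain in the tails, the protocol's figure would hold. What counts against it is the SAP's statement of what was used.

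Four stronger readings are tempting, and the documents do not support them.

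- **Phase 2 precision is overstated throughout.** The 1.36-fold figure is correct and identical in both documents.
- **The wrong 5% causes the optimistic half-width.** Both half-widths are stated for 108 evaluable participants, after losses, so the loss rate does not enter them.
- **The SAP's 13.3% shows that some strain has an SCR near 50%.** It is an upper bound, and could be a rounded worst case tied to no strain.
- **Table 20 is wrong.** Its cells are redacted and neither disputed figure is visible in it, so it can only be checked, not faulted.

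**Conclusion.** The point holds as a minor inconsistency with two separate parts.

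The 5% unevaluable rate is wrong on the protocol's own numbers: 120 and 108 imply 10%. This needs no assumption beyond the planned group size.

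The SCR half-width below 12% conflicts with the SAP's 13.3% for the same 108, a difference of 1.3 percentage points between the stated bounds. The conclusion that 12% is too favourable rests on SAP 4.8. The calculation supports it under equal rates, but cannot settle it without the redacted strain rates.

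No test, power or decision threshold depends on either figure, and neither enrolment nor the planned analyses change. This is not an undetected design error.

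**What to change.** In the text of protocol section 9.5.2, change the unevaluable rate from 5% to 10% and the SCR lower half-width from below 12% to below 13.3%, matching SAP 5.2. Check protocol Table 20 against SAP Table 8, and amend it only if the unredacted values differ. If no further protocol amendment is planned, a clarification or a note in the study report that cites SAP 4.8 and 5.2 would serve.

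Keep 120 enrolled and 108 evaluable per group. The cost is a wording change; the protocol's stated SCR precision becomes slightly less favourable.
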